12.4. Assessments: Listed by Each Study Day

12.4.1. Day -22 to Day -2: Screening Period

The Investigator will be expected to maintain a screening log of all potential study subjects. This log will include limited information about the potential subject and the date and outcome of the screening process (eg, enrolled into the study, reason for ineligibility, or refused to participate). The Investigator will provide information about the study to subjects who appear to meet the criteria for participation in the study.

During the screening period, the Investigator or qualified designee will obtain a medical history from each subject that includes relevant diagnoses and/or procedures/therapies with onset/resolutions dates. Medical histories should also include history of EFP (start date and family history), and history of tobacco and alcohol use (never, current, former).

Subjects meeting the relevant eligibility criteria listed in Section 11 may be enrolled in the study after the nature and purpose of the protocol have been explained and written informed consent to participate has been voluntarily provided by the subject or their legally authorized representative. The following procedures will be performed in sequential order and documented during the screening period:

1. Obtain written informed consent
2. Evaluate eligibility based on inclusion/exclusion criteria
3. Conduct live assessments of subject's cellulite severity in all 4 quadrants (left and right buttock, left and right posterolateral thigh) using the CR-PCSS
4. Medical history including EFP history
5. Record prior and concomitant medications/procedures
6. Physical examination including measurement of body weight, height, and evaluation of the Fitzpatrick skin type
7. Vital sign measurements
8. 12-lead ECG
9. Collection of samples for:
 - a. Clinical laboratory testing
 - b. Pregnancy testing
 - c. Alcohol breath test
 - d. Urine drug screen
10. Monitor AEs

12.4.2. Day -1: Admission to the Clinical Research Unit

Subjects will be admitted to the clinic for the inpatient period on the afternoon of Day -1. The following procedures will be performed and documented:

1. Re-evaluate eligibility based on inclusion/exclusion criteria
2. Record prior and concomitant medications/procedures
3. Vital sign measurements
4. Pregnancy test
5. Alcohol breath test
6. Urine drug screen
7. Monitor AEs

12.4.3. Day 1: Pre-dose and Dosing Activities

On Day 1, a 10-mL blood sample will be collected prior to dosing to document any baseline plasma levels of AUX-I and AUX-II.

In addition, 3 × 5-mL blood samples will be collected as a baseline sample for baseline anti-AUX-I/anti-AUX-II antibody levels/neutralizing antibodies to AUX-I and AUX-II in serum; if it is later determined that antibody assays are warranted based on clinical findings and/or PK results.

Dimples to be treated will be selected and marked and subjects will then be dosed in the 4 quadrants as detailed in Section [10.5](#).

Adverse events and concomitant medications will be recorded throughout the study.

12.4.4. Day 1: Care Procedures After CCH Injections

Immediately after injection, the Investigator or qualified designee will apply pressure to the injection sites for 3 minutes. Additionally, to evaluate the subject for possible immediate immunological AEs, the subject will remain in direct observation of medical personnel who are skilled in the management of acute allergic reactions for the first 30 minutes after receiving an injection of study drug (see Section [10.5](#)). A loose bulky gauze dressing may then be applied to the injection areas. Study personnel will remove the dressing in the evening to inspect the injection areas for edema and bruising.

During the first 30 minutes following injection, the subject will be monitored for:

- Signs of an immunological or other clinically significant systemic or local AEs
- Stable vital signs (see [Table 5](#))

Subjects will also be informed as follows:

- Your injection areas may appear bruised and/or swollen
- You may have moderate pain

12.4.5. Day 1: Pharmacokinetic Sampling Post Dose

Collection of blood samples for PK assessment will begin at 5 minutes following the last injection of study drug. Samples (10 mL each) will be collected at the following time points after the last injection on Day 1: at 5, 10, 20, and 30 minutes and 1, 2, 4, 8 and 12 hours after dosing. Blood samples are to be collected within 10% of the nominal time. The exact time of collection will be noted in the source document and eCRF.

12.4.6. Day 2: Discharge from the Research Unit

On the morning of Day 2, the 24-hour PK blood sample will be collected. Subjects will be given breakfast, have their vital signs measured, and be assessed for any AEs (such as site reactions in the dosing areas or any other AE). Beginning on Day 2 and continuing through the outpatient period, subjects will also be instructed as follows:

- Take over-the-counter (OTC) pain medications (eg, acetaminophen) if needed for pain

- If you have severe pain or severe swelling, or any other symptoms, tell your study doctor

Subjects will then be discharged from the clinical research unit.

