8.3. Summary of Known Risks and Benefits

A summary of safety risks is provided in the IB ([Endo, 2017](#)). The following events have been commonly observed: local injection site reactions (injection site bruising, injection site swelling, and injection site pain) for the various approved indications as well as those being investigated. In the phase 2b study of CCH in women with EFP, the following treatment related AEs were reported in $\geq 2\%$ of 189 CCH-treated women: injection site bruising (75.1%), injection site pain (59.3%), injection site nodule (14.3%), injection site pruritus (11.1%), injection site swelling (7.4%), injection site induration (5.8%), injection site mass (5.3%), injection site discoloration (3.2%), and injection site erythema (2.1%). These events are similar to events reported in the clinical trials of EN3835 for the approved indications. Postmarketing safety data are consistent with safety data reported in clinical trials.

Although a thorough benefit of CCH has not been fully evaluated in the treatment of EFP, the efficacy results from the Phase 2b study and previous EFP studies warranted further development.

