12.5. Prior and Concomitant Medications and Procedures

All medications (including OTC medication) administered to or taken by the subject within 3 months prior to the Screening visit will be recorded.

Subjects cannot be taking antiplatelet agents or anticoagulants (except for ≤ 150 mg aspirin daily) within 7 days before and after the dosing administration. Thereafter, any changes in concomitant medications or new medications added will be recorded.

Any diagnostic, therapeutic, or surgical procedure performed before the study period, including those for the treatment of EFP, should be recorded including the date, indication for, and description of the procedure.

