12.5.1. Prohibited Medications or Procedures

The following medications are prohibited during the study: anticoagulants, (warfarin, heparin, direct thrombin inhibitors, Factor X inhibitors) and antiplatelet agents (aspirin >150 mg/day and P2Y12 inhibitors, such as clopidogrel), which can cause additional bruising. However, the use of aspirin at a dose level of ≤ 150 mg per day will be permitted during the study.

Table 3: Concomitant Medication Restrictions

Drug Class	Restrictions
Anticoagulants	Subjects cannot be taking antiplatelet agents or anticoagulants (except for ≤ 150 mg aspirin daily) within 7 days before and after the dosing administration.

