3.9. Prior/Concomitant Medications and Procedures

Any medications (including OTC medication) taken during the study or within 3 months prior to the Screening visit will be recorded.

Any diagnostic, therapeutic, or surgical procedure performed before the study or during the study, including the treatment of EFP will be recorded.

Prohibited Medications: Subjects are prohibited to take antiplatelet agents (aspirin>150 mg/day and P2Y12 inhibitors, such as clopidogrel) or anticoagulants (warfarin, heparin, direct thrombin inhibitors) within 7 days before and after the dosing administration.

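### The discharge advice on over-the-counter painkillers does not carry the protocol's own aspirin restriction, which covers at least Days 2 to 8

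*Protocol*

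**What the plan says.** Protocol Section 12.4.6 sets out what subjects are told when they leave the research unit. The timing is explicit: "Beginning on Day 2 and continuing through the outpatient period, subjects will also be instructed as follows". The first item is "Take over-the-counter (OTC) pain medications (eg, acetaminophen) if needed for pain". The second asks them to report severe pain, severe swelling or other symptoms. Neither mentions aspirin or antiplatelet agents, and the section does not refer to Section 12.5.1.

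The restriction stands elsewhere, with two different durations:

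- Section 12.5.1 opens with "The following medications are prohibited during the study: anticoagulants, (warfarin, heparin, direct thrombin inhibitors, Factor X inhibitors" and goes on to "antiplatelet agents (aspirin >150 mg/day and P2Y12 inhibitors, such as clopidogrel), which can cause additional bruising". Aspirin up to 150 mg per day stays permitted.
- Section 12.5, repeated in Table 3, says: "Subjects cannot be taking antiplatelet agents or anticoagulants (except for ≤ 150 mg aspirin daily) within 7 days before and after the dosing administration".
- SAP Section 3.9 names the same aspirin threshold and applies it "within 7 days before and after the dosing administration".

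Protocol Section 12.4.4 tells subjects on Day 1 to expect bruising or swelling and possibly moderate pain, but nothing about which painkillers to avoid. Sections 12.4.7 to 12.4.9 have the site ask at Days 3, 8 and 22 what has been taken.

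**The concern.** The person who acts on Section 12.4.6 is the subject at home, who does not have Section 12.5.1 in front of her. If she is told that over-the-counter pain medication is acceptable and is given one example, she has no reason in that advice to avoid aspirin. The questions at later visits can detect such use but cannot prevent it.

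Two things are at stake. The first is the safety description. Safety is a primary objective (Protocol Section 9.1), and injection-site bruising is the most frequent treatment-related event cited from the Phase 2b study (75.1% of 189 treated women, Section 8.3). Bruising is also the harm that the restriction is meant to limit. With one open-label group and no control, a painkiller's contribution to bruising cannot be separated by comparison. The second is the subject's standing in the trial. Use of a prohibited medication is among the possible deviation types in SAP Section 4.2 and is an example reason for discontinuation in Protocol Section 11.3. She could incur either by doing what the site told her.

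**Working it through.** The plan states no figure on this point, so the check sets the passages side by side and then asks which results could move.

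1. **Do the advice and the restriction cover the same days?** Dosing is on Day 1 and the last visit is Day 22. The advice runs from Day 2 to Day 22.
   - Restriction to 7 days after dosing (Section 12.5, Table 3, SAP Section 3.9): it ends on Day 1 + 7 = Day 8. Overlap is Days 2 to 8, or 8 − 2 + 1 = 7 days.
   - Restriction for the whole study (Section 12.5.1): overlap is Days 2 to 22, or 22 − 2 + 1 = 21 days.
   
   They overlap on either reading. Only Days 9 to 22 depend on which duration governs.

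2. **Can the advice lead to restricted use?** This needs one fact the documents do not state: that aspirin is sold over the counter as a painkiller. I take it as an assumption. The documents give no tablet strengths either. Over an assumed range of 75 to 650 mg per unit, the fewest units that exceed 150 mg in a day are:
   - 75 mg: 3 units (225 mg)
   - 81 mg: 2 units (162 mg)
   - 100 mg: 2 units (200 mg)
   - 300 mg or more: 1 unit
   
   Ordinary use for pain could therefore pass the threshold. A subject who takes only acetaminophen breaches nothing.

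3. **Which bruising results could move?** Incidence has limited room. Staff inspect the injection areas for bruising on the evening of Day 1 (Section 12.4.4), before the advice begins, and a subject is counted once per preferred term (Protocol Section 16.6.4, SAP Section 7.9.2). A subject already bruised on Day 1 cannot add to incidence later. If the Phase 2b rate applied unchanged, 0.751 × 12 = 9.0 subjects would bruise anyway, leaving about 12 − 9 = 3. That rate comes from up to three sessions in one quadrant, so it is only a rough guide for a single dose in four quadrants.

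   Severity and duration have more room. Section 14.4 records the greatest intensity reached in a continuous episode. SAP Section 7.9.2 tabulates events by severity, and drug-related events by duration (under 14, 14 to 21, over 21 days). Each subject who changes category moves that row by 1/12 = 8.3 percentage points.

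4. **What follows for the subject's data?** Under SAP Section 4.2 the study team classes each deviation as major or minor and decides at the deviation meeting whether subjects with major ones stay in the analysis populations. Discontinued subjects are not replaced (Protocol Section 11.3.3), and the plan is 12 enrolled with at least 10 completing (Section 16.1), a margin of 2.

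**The case against.** The strongest reply is that there is no contradiction. The advice is permissive, its one named drug is not restricted, and Section 12.5.1 is a specific rule in the same chapter that the site must also apply. Read together, over-the-counter pain relief is allowed subject to the restriction. Exclusion criterion 3 already removes anyone who needs antiplatelet medication during the trial, and eligibility is rechecked on Day −1. The consent form and any subject leaflet are not in the public documents and may carry the warning.

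Much of this stands. The advice permits a breach and does not require one, and the documents cannot show that subjects go unwarned. But the site can read both sections while the subject hears only the advice, and exclusion criterion 3 does not tell an eligible subject which painkiller to avoid after discharge.

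Two stronger readings are tempting and not supported:

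- A reader might multiply the 59.3% injection-site pain rate in Section 8.3 by 12 and conclude that about 7 subjects are at risk. That rate comes from a study with three treatment visits about 21 days apart, whereas this is a single dose. It includes pain that may resolve on Day 1, before the advice starts. It also says nothing about how many subjects would take a painkiller, let alone aspirin.
- A reader might conclude that any extra bruising would be attributed to the study drug. The investigator judges causality event by event (Section 14.3), and concomitant medications are recorded at every visit and tabulated and listed (SAP Section 7.6). Misattribution is possible but not certain.

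**Conclusion.** The point holds as a gap between the advice given to subjects and the protocol's own restriction. The overlap is certain for Days 2 to 8. For Days 9 to 22 it depends on which of the two stated durations governs. Following the advice as written could lead to use of a prohibited medication, with possible effects on the severity or duration of bruising and a possible recorded deviation.

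The number of subjects affected is unknown and could be zero. The conclusion assumes that aspirin is available over the counter as a painkiller and that no other material, such as the consent form, passes the restriction on. No effect on the pharmacokinetic objective has been shown, beyond the possibility that a deviation classed as major affects a subject's inclusion. The gap is modest, but worth closing because it concerns what subjects are told to do and costs almost nothing to correct.

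**What to change.** Reconcile Protocol Section 12.4.6 with Sections 12.5 and 12.5.1, Table 3 and SAP Section 3.9, so that the painkiller advice given at discharge carries the protocol's existing restriction by direct cross-reference. In the same edit, settle the two stated durations so that all these passages agree. Which agents, limits and duration apply is for the sponsor's medical team; this review proposes none. Check that the consent form and any subject handout say the same.

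The cost is one sentence in Section 12.4.6, aligned wording on duration, and the matching line in the subject instruction. No visit, sample or analysis is added.

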12.4.7. Day 3: Follow-up Outpatient Visit

On the morning of Day 3, subjects will return to the clinical research unit as an outpatient for the collection of the 48-hour post-dose PK blood sample. Subjects will have their vital signs measured, be assessed for any AEs, have the dosing areas checked, and questioned about taking any concomitant medications. Subjects will then be discharged from the clinical research unit and will be instructed when to return. The site will schedule the Day 8 visit.

12.4.8. Day 8: Follow-up Outpatient Visit

On the morning of Day 8, subjects will return to the clinical research unit as an outpatient for the collection of the 168-hour post-dose PK blood sample. Subjects will have their vital signs measured, be assessed for any AEs, have the dosing areas checked, and questioned about taking any concomitant medications. Subjects will then be discharged from the clinical research unit and will be instructed when to return. The site will schedule the Day 22 visit.

12.4.9. Day 22: End of Study Outpatient Visit

On the morning of Day 22, subjects will return to the clinical research unit as an outpatient for the end of study visit. At this visit, the 504-hour post-dose PK blood sample will be collected. In addition, the 3×5 -mL blood samples for potential determination of anti-AUX-I/anti-AUX-II antibody levels/neutralizing antibodies to AUX-I and AUX-II in serum will be collected; antibody assays will be conducted only if clinical findings and/or PK results warrant the assays.

The cellulite severity assessments of each of the 4 treated quadrants using the CR-PCSS (live assessment) will be completed by the Investigator (or designee) at this end of study visit.

Subjects will have their vital signs measured, be assessed for any AEs, and questioned about taking any concomitant medications. The body weight will also be taken. Before they are discharged from the study, they will have a blood draw for clinical laboratory tests.

Following completion of all study related assessments and procedures; subjects will then be discharged from the clinical research unit.

12.5. Prior and Concomitant Medications and Procedures

All medications (including OTC medication) administered to or taken by the subject within 3 months prior to the Screening visit will be recorded.

Subjects cannot be taking antiplatelet agents or anticoagulants (except for ≤ 150 mg aspirin daily) within 7 days before and after the dosing administration. Thereafter, any changes in concomitant medications or new medications added will be recorded.

Any diagnostic, therapeutic, or surgical procedure performed before the study period, including those for the treatment of EFP, should be recorded including the date, indication for, and description of the procedure.

12.5.1. Prohibited Medications or Procedures

The following medications are prohibited during the study: anticoagulants, (warfarin, heparin, direct thrombin inhibitors, Factor X inhibitors) and antiplatelet agents (aspirin >150 mg/day and P2Y12 inhibitors, such as clopidogrel), which can cause additional bruising. However, the use of aspirin at a dose level of ≤ 150 mg per day will be permitted during the study.

Table 3: Concomitant Medication Restrictions

Drug Class	Restrictions
Anticoagulants	Subjects cannot be taking antiplatelet agents or anticoagulants (except for ≤ 150 mg aspirin daily) within 7 days before and after the dosing administration.

12.5.2. Prohibited Procedures

The treatments and procedures listed in exclusion criteria [6](#) are prohibited during the study.

12.6. Treatment Compliance

All subjects will receive study drug administered by a clinician in the clinical research unit.

Accidental or intentional overdoses should be reported to the Sponsor/designee promptly (see Section [14.6.2.1](#)).

12.7. Blinding and Randomization

This study will be conducted as an open-label investigation; no blinding of assigned treatment will occur.

13. ASSESSMENT OF CELLULITE SEVERITY

13.1. Cellulite Severity Analysis

Cellulite severity will be assessed by the Investigator's rating of cellulite severity using the CR-PCSS. Evaluations will be done on each of the 4 quadrants at Screening and Study Day 22.

14. ASSESSMENT OF SAFETY

14.1. Definitions

14.1.1. Adverse Events

An AE is any unfavorable or unintended change in body structure (signs), body function (symptoms), laboratory result (eg, chemistry, ECG, X-ray, etc), or worsening of a preexisting condition associated temporally with the use of the study medication whether or not considered related to the study medication. AEs will be captured once a subject has signed the informed consent. AEs include:

- Changes in the general condition of the subject
- Subjective symptoms offered by or elicited from the subject
- Objective signs observed by the Investigator or other study personnel
- All concurrent diseases that occur after the start of the study, including any change in severity or frequency of preexisting disease
- All clinically relevant laboratory abnormalities or physical findings that occur during the study

A TEAE is any condition that was not present prior to treatment with study medication but appeared following treatment, was present at treatment initiation but worsened during treatment, or was present at treatment initiation but resolved and then reappeared while the individual was on treatment (regardless of the intensity of the AE when the treatment was initiated).

All AEs, including observed or volunteered problems, complaints, signs or symptoms must be recorded on the AE page of the eCRF, regardless of whether associated with the use of study medication. This would include AEs resulting from concurrent illness, reactions to concurrent medication use, or progression of disease states. A condition present at baseline that worsens after initiation of study treatment will be captured as an AE; the onset date will be the date the event worsened. The AE should be recorded in standard medical terminology when possible.

14.1.2. Serious Adverse Events

A SAE is defined as an AE that:

- Results in death
- Is immediately life-threatening (there is an immediate risk of death from the AE as it occurred; this does not include an AE that had it occurred in a more serious form may have caused death)
- Results in or prolongs an inpatient hospitalization (Note: a hospitalization for elective or pre-planned surgery, procedure, or drug therapy does not constitute an SAE)
- Results in permanent or substantial disability (permanent or substantial disruption of one's ability to conduct normal life functions)

- Is a congenital anomaly/birth defect (in offspring of a subject using the study medication regardless of time to diagnosis)
- Is considered an important medical event

Important medical events are defined as events that, based upon appropriate medical judgment, may jeopardize the subject and may require medical or surgical intervention to prevent one of the other serious outcomes. Examples of important medical events include allergic bronchospasm requiring intensive treatment in an emergency room or at home, blood dyscrasias or convulsions that do not result in inpatient hospitalization, or the development of drug dependency or drug abuse.

